### **3.0 RISK ANALYSIS**

#### **3.1 Anticipated risks**

The primary physical risks of this study are

- 1) the pessary fails to reduce preterm birth
- 2) cervical amputation due to tight pessary constriction of the cervix
- 3) erosion of maternal tissue
- 4) maternal discomfort
- 5) vaginal infections
- 6) vaginal discharge, which may be mistaken for rupture of membranes
- 7) pain at insertion and/or removal
- 8) improper pessary placement

The risks are minimized by

- 1) This clinical trial is conducted after a large Spanish RCT suggested that the pessary is a better treatment than any current therapy. Rather than testing the pessary for the first time, our trial has the goal of confirming the prior Spanish results in a Midwest USA regional setting.
- 2) Patients are evaluated every 2 weeks for symptoms of pain, abnormal vaginal discharge, and infections. A questionnaire is completed, and a speculum exam to directly assess the cervical and vaginal tissue is performed as needed. Nitrazine, ferning, and pooling will be performed as needed to diagnosed rupture of membranes correctly. The pessary is removed if there are concerning signs of trauma, erosion, intractable pain, and bleeding. The NAMSA report reiterates the known safety of silicone pessaries (p8-9, 10-11).
- 3) Providers are taught how to insert and remove the pessary by instructional videos sponsored by [name], the inventor of the device. In addition, pain

experienced at insertion and/or removal will be treated with narcotic administration as needed.

Risk benefit analysis:

This study is conducted to confirm results of a larger RCT already concluded internationally. Those results strongly suggest that the pessary is more effective than any current therapy. These potential benefits outweigh the concerns for untreated short cervix with resulting preterm birth. The concern of tissue erosion is extremely low (please reference NAMSA report, p8-9, 10-11). These benefits accrue directly to the individual, and in aggregate, to society as a result.

### 3.2 Adverse event reporting

#### 3.2.1 Adverse event definitions

**Unanticipated adverse device effect (UADE):** Any serious adverse effect on health or safety or any life-threatening problem or death caused by, or associated with, a device, if that effect, problem, or death was not previously identified in nature, severity, or degree of incidence in the investigational plan or IDE application (including a supplementary plan or application), or any other unanticipated serious problem associated with a device that relates to the rights, safety, or welfare of subjects.

**Associated with the investigational device:** There is a reasonable possibility that the adverse effect may have been caused by the investigational device.

**Life-threatening adverse effect:** Any adverse effect that places the subject, in the view of either the investigator or the sponsor, at immediate risk of death from the effect **as it occurred**. It does not include a reaction that, had it occurred in a more severe form, might have caused death.

**Serious adverse effect:** An adverse effect is considered “serious” if, in the view of either the investigator or the sponsor, it results in any of the following outcomes:

- death
- a life-threatening AE
- inpatient hospitalization or prolongation of existing hospitalization
- a persistent or significant disability/incapacity
- a congenital anomaly/birth defect.

**Unanticipated adverse effect:** Any adverse effect, the nature, specificity, severity, or frequency of which is not consistent with the risk information in the clinical study protocol or elsewhere in the current IDE application.

#### 3.2.2 Eliciting adverse effect information

Clinical study subjects will be routinely questioned about adverse effects at study visits.

#### 3.2.3 Recording and assessment of adverse effects

All observed or volunteered adverse effects (serious or non-serious) and abnormal test findings, regardless of treatment group, if applicable, or suspected causal relationship to

the investigational device or, if applicable, other study treatment or diagnostic product(s) will be recorded in the subjects' case histories. For all adverse effects, sufficient information will be pursued and/or obtained so as to permit 1) an adequate determination of the outcome of the effect (i.e., whether the effect should be classified as a *serious adverse effect*) and; 2) an assessment of the casual relationship between the adverse effect and the investigational device or, if applicable, the other study treatment or diagnostic product(s).

Adverse effects or abnormal test findings felt to be associated with the investigational device or, if applicable, other study treatment or diagnostic product(s) will be followed until the effect (or its sequelae) or the abnormal test finding resolves or stabilizes at a level acceptable to the sponsor-investigator.

#### **3.2.4 Abnormal test findings**

An abnormal test finding will be classified as an *adverse effect* if one or more of the following criteria are met:

- The test finding is accompanied by clinical symptoms
- The test finding necessitates additional diagnostic evaluation(s) or medical/surgical intervention; including significant additional concomitant drug or other therapy (Note: simply repeating a test finding, in the absence of any of the other listed criteria, does not constitute an adverse effect.)
- The test finding leads to a change in study dosing or exposure or discontinuation of subject participation in the clinical study
- The test finding is considered an adverse effect by the sponsor-investigator

#### **3.2.5 Causality and severity assessment**

The sponsor-investigator will promptly review documented adverse effects and abnormal test findings to determine 1) if the abnormal test finding should be classified as an adverse effect; 2) if there is a reasonable possibility that the adverse effect was caused by the investigational device or other study treatments; and 3) if the adverse effect meets the criteria for a *serious adverse effect*.

If the sponsor-investigator's final determination of causality is "unknown and of questionable relationship to the investigational device or other study treatments," the adverse effect will be classified as *associated with the use of the investigational device or other study treatments* for reporting purposes. If the sponsor-investigator's final determination of causality is "unknown but not related to the investigational device or other study treatments," this determination and the rationale for the determination will be documented in the respective subject's case history.

#### **3.2.6 Reporting adverse effects to the FDA**

For any observed or volunteered adverse event that is determined to be a UADE, the sponsor-investigator will submit an expedited safety report to the FDA's Center for Devices and Radiological Health. The expedited safety report will consist of:

- a completed [Form FDA 3500A](#)

- a cover letter analyzing the significance of the event

A copy of this safety report will be provided to all participating study investigators.

The completed [Form FDA 3500A](#) and cover letter will be submitted to the FDA as soon as possible and, in no event, later than 10 working days after the sponsor-investigator first receives notice of the adverse effect.

If, following receipt and investigation of follow-up information regarding an adverse effect that was previously determined not to be a UADE, the sponsor-investigator determines that the event does meet the requirements for expedited reporting, the sponsor-investigator will submit a completed [Form FDA 3500A](#) and cover letter as soon as possible, but in no event later than 10 working days, after the determination is made.

Subsequent to the initial submission of a completed [FDA Form 3500A](#), the sponsor-investigator will submit additional information concerning the reported adverse effect as requested by the FDA.

### **3.2.5 Reporting adverse effects to the responsible IRB**

For any adverse event determined to be a UADE, the sponsor-investigator will submit the completed [Form FDA 3500A](#) and cover letter to the IRB as soon as possible and, in no event, later than 10 working days after the sponsor-investigator first receives notice of the adverse effect.

Follow-up information to reported adverse effects will be submitted to the IRB as soon as the relevant information is available.

### **3.3 Withdrawal of subjects due to adverse effects**

Patients are evaluated every 2 weeks for symptoms of pain, abnormal vaginal discharge, and infections. A questionnaire is completed, and a speculum exam to directly assess the cervical and vaginal tissue is performed as needed. Nitrazine, ferning, and pooling will be performed as needed to diagnosed rupture of membranes correctly. The pessary is removed if there are concerning signs of trauma, erosion, intractable pain, and bleeding.

Patients whose pessaries are removed are still analyzed in their assigned group according to an intent-to-treat analysis. Their outcomes and complications are recorded similar to other subjects. They are not replaced.

## **4.0 DESCRIPTION OF THE INVESTIGATIONAL DEVICE**

Please see NAMSA report for description of cytotoxicity, sensitization, irritation, acute systemic toxicity, subchronic systemic toxicity, genotoxicity, implantation, chronic systemic toxicity in detail.

In this study, the Arabin pessary will be for single patient use only. Each enrolled patient will be given their own new pessary. The patient will use the same pessary throughout the length of the study.

Please see MEDCERT certificates for information regarding manufacturing, quality management, and distribution. Pessaries are stored at room temperature and do not require special packaging. The principal investigators “install” the pessaries after they are appropriately trained by a video tutorial.

The following description is *modified* from <http://www.dr-arabin.de/e/cerclage/html>

The Arabin pessary is a ring manufactured from medical grade silicone. It has outer and inner diameters that vary, a height when laid flat, and a curvature to one side of the pessary. The width of the outer and inner diameters are chosen depending on the individual constitution of the pregnancy patient. The curvature of the pessary is upwards so that the pelvic floor supports the larger diameter. The smaller, inner diameter encompasses the cervix. After application the pessary changes the inclination of the cervical canal, directing it more posteriorly (figure 1). Thus the weight of the pregnancy is more on the anterior lower segment, as can be observed by TVS in selected cases. The use of a spreading gliding compound facilitates pessary insertion. The silicone material is inert and does not react with the vaginal epithelium or cervical epithelium. The silicone pessary does not change during its placement in the vaginal canal. In general, singleton pregnancies require a pessary height of 21-25 mm, and multiple pregnancies require a pessary height of 25-30 mm.

There are 13 sizes of the Arabin cervical pessary, differing by their outer diameter, inner diameter, and height. The investigators will be appropriately trained according to instructional videos. If insufficient, there are provision plans to be trained in person by the manufacturer. The pessary size will be selected based on a best fit to the patient’s anatomy. This proper fit will help obviate the risk of cervical amputation.

[figure not shown]

Figure 1

## 5.0 MONITORING PROCEDURES

Independent monitoring of the study for compliance with the clinical protocol and with IDE regulations will be conducted periodically by qualified staff of the University of Kansas Medical Center. The data from both sites will be reviewed every 6 months by the designated medical monitor for the study, [name] MD. [name] will not be blinded as he is searching for adverse events occurring in the pessary group. In addition, [name] MD and [name] RN, a research coordinator assigned to the study, will conduct monthly chart audits at KUMC to compare clinic, hospital, and research records for accuracy of data entry. [name] MD will conduct monthly chart audits at MUSC. If an adverse event is encountered, reporting to the Human Subjects Committee (HSC) at KUMC and the FDA will occur as detailed in section 3.2. Principal investigators who are notified of possible adverse events will also proceed as detailed in section 3.2.

Medical Monitor Contact Information:

[name]

Neonatologist

University of Kansas Medical Center

[name]

[name]

[contact]

Email: [[contact]](mailto:[contact])

[contact]

The medical monitor is specifically chosen outside of the department of OBGYN to allow for objectivity.

Adverse events which would require immediate suspension of study for review would include an excess of 1 maternal death, 1 maternal ICU admission for sepsis, or 2 perinatal deaths in the **pessary** group.

Unanticipated adverse events will be reported immediately to the HSC, and its recommendations for temporary cessation or continuation of the study will be followed. If an excess of 4 perinatal deaths occur in the **pessary** group, the study should be concluded.

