PLANNED INTERIM ANALYSES	The data will be reviewed every 6 months by the designated medical monitor for the study, [name] MD (neonatologist). The medical monitor is specifically chosen outside of the department of OBGYN to allow for objectivity. Adverse events which would requires immediate suspension of study for review would include an excess of 1 maternal death, 1 maternal ICU admission for sepsis, or 2 perinatal deaths in the pessary group. Unanticipated adverse events will be reported immediately to the Human Subjects Committee (HSC) and the FDA, and its recommendations for temporary cessation or continuation of the study will be followed. If an excess of 4 perinatal deaths occur in the pessary group, the study should be concluded.

STATISTICS Primary Analysis Plan	
The Research hypothesis is that proportion of preterm deliveries before 37 weeks 0 days gestation is reduced in the pessary group as compared to the control group. The primary endpoint and the categorical outcomes that are part of the secondary endpoints will be reported using frequency counts and proportions. For the secondary endpoints that are continuous variables, summary statistics such as mean and standard deviation, or median and inter-quartile range will be reported based on whether the assumption of normality is justified. A chi-square test (or a Fisher's exact test) will be used to perform statistical comparison of proportions across the two groups. Likewise, comparisons for continuous outcomes will be done using a two-sample t-test (or Wilcoxon Rank Sum test) as will be deemed necessary. For gestational age, we will also compare the Kaplan Meier survival curves of the two groups (control and pessary) using the logrank test. Level of significance for all statistical tests will be set at 0.05.

Rationale for Number of Subjects	
Based on KUMC and MUSC hospital data, the proportion of preterm births before 37 weeks 0 days gestation in patients with short cervixes is 30%. In order to detect a reduction in half to 15%, a sample size of 242 will be required to have power of 80% using a two-sided z-test assuming pooled variances. Level of significance is set at 0.05. We anticipate a loss to follow up rate of 5%. We expect to enroll 256 subjects.

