#### 1.4.2 Secondary Objectives

- Neonatal composite morbidity – fetal or neonatal death, respiratory distress syndrome (RDS), chronic lung disease, periventricular lucency, periventricular leukomalacia, intraventricular hemorrhage grade 3 or 4, necrotizing enterocolitis, early-onset-culture-proven sepsis
- Neonatal length of stay
- Neonatal NICU admission
- Total NICU days
- Duration of ventilator support
- retinopathy of prematurity (ROP) requiring treatment
- birthweight < 1500g and < 2500g
- preterm birth < 34 weeks
- gestational age at delivery
- use of tocolysis
- use of antenatal steroids
- chorioamnionitis
- vaginal bleeding
- preterm premature rupture of membranes
- cesarean delivery

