#### 1.5 Anticipated duration of the clinical investigation

KUMC examines approximately 1900 patients in a year for cervical length screening in the 2nd trimester (our standard of care for more than 6 years). Approximately 45 patients a year have cervical lengths < 25 mm.

MUSC examines approximately 2-3 thousand patients per year with cervical length screening. Approximately 60 patients a year have cervical lengths <25 mm.

We expect 80% accrual rate into the study. The expected duration of the study is ~ 4 years.

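### Do the safety triggers need rewriting because the protocol does not define an excess of N events?

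*Combined protocol and SAP*

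**What the plan says.** Section 5.0 (Monitoring Procedures) lists pessary-arm events that call for "immediate suspension of study for review would include an excess of 1 maternal death, 1 maternal ICU admission for sepsis, or 2 perinatal deaths". It then gives a conclusion trigger for the same arm, which opens "If an excess of 4 perinatal deaths occur in the"; once it is met, the study ought to end. The Protocol Synopsis, under Planned Interim Analyses, has the same suspension list for that arm ("would include an excess of 1 maternal death, 1 maternal ICU admission for sepsis, or 2 perinatal deaths in the") and the same conclusion sentence.

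The surrounding arrangements are:

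- **Review.** The Synopsis states: "The data will be reviewed every 6 months by the designated medical monitor for the study". Section 5.0 adds that the data come from both sites and that the monitor is unblinded because "he is searching for adverse events occurring in the pessary group".
- **Ethics committee.** Section 5.0 says: "Unanticipated adverse events will be reported immediately to the HSC, and its recommendations for temporary cessation or continuation of the study will be followed".
- **Recording.** Section 3.2.3 has adverse effects recorded whatever the treatment group.
- **Endpoints.** The secondary composite in Section 1.4.2 begins with "fetal or neonatal death, respiratory distress syndrome (RDS), chronic lung disease", so deaths are foreseen in both arms.

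No section defines an excess, names a comparator for it, or says which event sets off the trigger.

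**The concern.** In a randomised trial, an excess usually means more than in the comparison group. Here it could also mean simply more than a stated number in the pessary arm. A second question is separate from the first: whether reaching the number is enough, or whether it must be passed.

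The readings can call for different actions on identical data, and no single reading is always the stricter. If the word means a pessary-arm count, the study could reach its conclusion trigger while the control arm has as many deaths or more. If it means a difference, a run of pessary-arm deaths matched in control would trigger nothing. A rule that can end a trial ought to be applied in one way, and it is uncomfortable to settle its meaning once deaths by arm are known.

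**Working it through.** **1. Inputs.** Section 2.4.2 plans 256 women at 1:1, so 256 / 2 = 128 per arm. Section 1.5 says "The expected duration of the study is ~ 4 years"; six-monthly review over 4 years gives 8 looks, or 128 / 8 = 16 women per arm between looks. The conclusion number is 4 (Section 5.0). The documents give no perinatal death rate, so equal true rates of 1 to 5% in both arms are assumed. They also give no operating figure for the triggers, so there is nothing of the plan's own to reproduce here.

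**2. Divergence without any assumed rate.** Let X be pessary-arm and Y control-arm perinatal deaths.

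| X | Y | Count, more than 4 | Difference, at least 4 | Difference, more than 4 |
|---|---|---|---|---|
| 5 | 5 | met | not met (0) | not met (0) |
| 4 | 0 | not met | met (4) | not met (4) |
| 5 | 0 | met | met (5) | met (5) |

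The first row isolates the comparator. The second mixes comparator and inequality: under a count of at least 4, that row would also be met.

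**3. How often each threshold is reached with no true difference.** X and Y are independent Binomial(128, p). Expected pessary-arm deaths are 128p: 1.28 at 1%, 3.84 at 3%, 6.4 at 5%. The count columns are P(X ≥ k). The one-look columns are P(X − Y ≥ k), summed over the joint distribution at full enrolment. The eight-look columns are the exact probability that X − Y reaches k at any of eight looks. Entries are percentages.

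| p | X ≥ 5 | X ≥ 4 | X − Y ≥ 5, one look | X − Y ≥ 4, one look | X − Y ≥ 5, eight looks | X − Y ≥ 4, eight looks |
|---|---|---|---|---|---|---|
| 1% | 1.0 | 4.0 | 0.3 | 1.5 | 0.4 | 1.7 |
| 2% | 11.5 | 25.4 | 2.2 | 5.7 | 2.7 | 7.3 |
| 3% | 33.9 | 53.7 | 4.9 | 9.7 | 6.3 | 13.2 |
| 4% | 58.4 | 75.7 | 7.4 | 13.0 | 10.0 | 18.2 |
| 5% | 77.2 | 88.7 | 9.7 | 15.6 | 13.4 | 22.3 |

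The natural pair is more than 4 in the pessary arm (X ≥ 5) against 4 more than control (X − Y ≥ 4). At 3% with eight looks these are 33.9% and 13.2%, a ratio of 33.9 / 13.2 ≈ 2.6. Setting X ≥ 5 against X − Y ≥ 5 gives 33.9 / 6.3 ≈ 5.4, which overstates the gap. At 1% the natural pair reverses: 1.0% for the count, 1.5% (one look) or 1.7% (eight looks) for the difference.

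**4. What the percentages are not.** They assume that the trial always resumes unchanged after suspension, that all women are enrolled and that all outcomes are known. On the count reading, suspension for review comes at the second or third pessary-arm perinatal death, before the fourth or fifth. P(X ≥ 3) is 13.7% at 1%, 74.2% at 3% and 95.7% at 5%, so the review would often be convened well before the conclusion trigger mattered. The table gives threshold crossings, not probabilities of ending the trial.

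**5. What the text itself supports.** The triggers name the pessary group, and the monitor's stated task is to look for events in that arm. No sentence mentions control. The ordinary reading is therefore a pessary-arm count, leaving mainly the choice between the Nth and the (N+1)th event.

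**The case for a change.** The strongest case for a change is that these are the only numeric stopping rules in the documents and nothing elsewhere supplies their meaning. A difference rule is workable: allocation is 1:1, the monitor is unblinded and control-arm events are recorded. Accepting the count reading still leaves the inequality open. At an assumed 3%, that alone moves the crossing probability from 33.9% to 53.7%. A first maternal death would not meet the listed trigger if it means more than one. The suspension review does not resolve the matter, since it relies on the same word, and a defining sentence would cost almost nothing.

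The ambiguity stands, in both comparator and inequality, and so does the arithmetic. The consequence is weaker than it appears. The suspension list is worded as open, so a first maternal death is not shown to escape review. Meeting the conclusion trigger means the study should end; no automatic stop is described, and suspension for review precedes it. The worry about settling the meaning after seeing allocation has little force, because the trial is open-label (Section 2.3.1) and the monitor is unblinded by design. A ceiling on pessary-arm deaths is a legitimate conservative choice for a device that Section 2.5.2 says lacks FDA approval, so the possibility of stopping without an imbalance is not itself a flaw. A table of crossing probabilities would change no action, and a formal look at both arms adds little for a monitor who already reviews the data unblinded.

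**Conclusion.** The wording is incomplete, but no change to the plan follows. What is missing is the comparator and the inequality behind one word. The named arm and the monitor's task point to a pessary-arm count, and what remains open would come before the monitor and the ethics committee at suspension, ahead of any conclusion. Rule and thresholds are the sponsor's to set, and nothing here shows them to be wrong.

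The size depends on a death rate that the documents neither give nor bound. Near 1% the readings hardly differ (1.0% against 1.5%); at 3% and 5% the threshold crossings differ substantially (33.9% against 9.7%, and 77.2% against 15.6%, at one look). All these figures assume equal risk, 128 per arm and resumption after every suspension. The cover statement reports that 7 women were enrolled and no tests were run, so there is no sign that the ambiguity affected conduct.
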